2.3 STUDY AIMS/HYPOTHESES

2.3.1 PRIMARY OUTCOME – WORKING MEMORY CAPACITY

RATIONALE. Participants make a button press on a keyboard to indicate if the probed items are matched or non-matched to the items held in memory. The investigators will calculate the accuracy for these responses and convert this to Pashler's working memory capacity metric for each condition. Theta oscillations are known to be generated in frontal cortex when cued to the contralateral visual field. Alpha oscillations are known to be generated in parietal cortex when cued to the ipsilateral visual field.

ALTERNATIVE HYPOTHESIS. When the frequency of TMS to either frontal or parietal cortex is compatible with the endogenous activity, working memory capacity should increase relative to TMS that is incompatible. Therefore, we will report the TMS compatibility effect as the average of "theta minus alpha TMS to frontal cortex for retro-cue right" and "alpha minus theta TMS to parietal cortex for retro-cue left". We will report the mean and standard deviation of the TMS compatibility effect across participants. This effect will be investigated using repeated-measures two-way ANOVA, and an interaction between TMS site and TMS frequency is hypothesized.

NULL HYPOTHESIS. There is no systematic effect of frequency specific TMS on working memory capacity.

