2.3.2 PRIMARY OUTCOME – SPECTRAL POWER

RATIONALE. The electrical activity of the brain is recorded during performance of the task and during brain stimulation. The investigators will perform Morelet wavelet convolution on the recorded electrical signal to calculate the spectral power of theta (5-8 hertz) and alpha (8-12 hertz). Theta oscillations are known to be generated in frontal cortex when cued to the contralateral visual field. Alpha oscillations are known to be generated in parietal cortex when cued to the ipsilateral visual field.

ALTERNATIVE HYPOTHESIS. When the frequency of TMS to either frontal or parietal cortex is compatible with the endogenous activity, spectral power in the stimulated frequency band should increase relative to TMS that is incompatible. Therefore, we will report the TMS compatibility effect as the average of "theta power for theta minus alpha TMS to frontal cortex for retro-cue right" and "alpha power for alpha minus

theta TMS to parietal cortex for retro-cue left". We will report the mean and standard deviation of the TMS compatibility effect across participants. This effect will be investigated using repeated-measures two-way ANOVA, and an interaction between TMS site and TMS frequency is hypothesized.

NULL HYPOTHESIS. There is no systematic effect of frequency specific TMS on spectral power.

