2.3.3 SECONDARY OUTCOME – RESPONSE TIME

RATIONALE. Participants make a button press on a keyboard to indicate if the probed items are matched or non-matched to the items held in memory. The investigators will calculate the response time for each condition. Theta oscillations are known to be generated in frontal cortex when cued to the contralateral visual field. Alpha oscillations are known to be generated in parietal cortex when cued to the ipsilateral visual field.

ALTERNATIVE HYPOTHESIS. When the frequency of TMS to either frontal or parietal cortex is compatible with the endogenous activity, response time should decrease relative to TMS that is incompatible. Therefore, we will report the TMS compatibility effect as the average of "theta minus alpha TMS to frontal cortex for retro-cue right" and "alpha minus theta TMS to parietal cortex for retro-cue left". We will report the mean and standard deviation of the TMS compatibility effect across participants. This effect will be investigated using repeated-measures two-way ANOVA, and an interaction between TMS site and TMS frequency is hypothesized.

NULL HYPOTHESIS. There is no systematic effect of frequency specific TMS on response time.

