11.1 STATISTICAL ANALYSIS STRATEGIES

To control for non-specific effects of rhythmic TMS, we will use an active control: arrhythmic TMS (randomized inter-pulse-interval) that is matched to the target stimulation in number of pulses and temporal duration. All analyses will be run on the difference from condition-matched arrhythmic TMS. The key analysis is a two-way repeated-measures ANOVA with factors TMS frequency (theta vs alpha) and location (inferior-IPS vs anterior-MFG). Post-hoc t-tests will be run on a significant main effect of TMS frequency, TMS site, or interaction. We will use Tukey's adjusted significance for post-hoc testing to correct for multiple comparisons.

Primary outcome: working memory capacity. Two-way repeated-measures ANOVA run on the difference from arrhythmic TMS with factors (TMS site and TMS frequency). The direction of the retro-cue is held consistent for each site: for TMS to frontal cortex (anterior-MFG) the retro-cue to the right is used, and for TMS to parietal cortex (inferior-IPS) the retro-cue to the left is used. We hypothesize that theta frequency rhythmic TMS will improve behavioral performance when applied to anterior-MFG; i.e. a main effect of TMS frequency and/or an interaction between TMS frequency and cue. We hypothesize that alpha frequency rhythmic TMS will improve behavioral performance for retro-cue trials when applied to inferior-IPS; i.e. an interaction between TMS frequency and cue.

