Primary outcome: Spectral power. We collected EEG recording during the delivery of rhythmic TMS. We hypothesize, based on previous studies with identical rhythmic TMS trains, that rhythmic TMS will entrain neural oscillations in the targeted frequency. We will quantify entrainment from rhythmic TMS by analyzing the spectral decomposition of the EEG signal during TMS and immediately after TMS. We will run a six-cycle Morlet wavelet convolution with the EEG signal to estimate spectral density (microvolts per hertz). We hypothesize that the amplitude of theta activity will be increased following theta rhythmic TMS relative to theta activity following arrhythmic TMS. Similarly, alpha amplitude will be increased following alpha rhythmic TMS relative to alpha amplitude following arrhythmic TMS. The direction of the retro-cue is held consistent for each site: for TMS to frontal cortex (anterior-MFG) the retro-cue to the right is used, and for TMS to parietal cortex (inferior-IPS) the retro-cue to the left is used. We hypothesize an interaction between TMS frequency and cue.

Primary outcome: response time. Two-way repeated-measures ANOVA run on the difference from arrhythmic TMS with factors (TMS site and TMS frequency). The direction of the retro-cue is held consistent for each site: for TMS to frontal cortex (anterior-MFG) the retro-cue to the right is used, and for TMS to parietal cortex (inferior-IPS) the retro-cue to the left is used. We hypothesize that theta frequency rhythmic TMS will improve behavioral performance (decreased response time) when applied to anterior-MFG; i.e. a main effect of TMS frequency and/or an interaction between TMS frequency and cue. We hypothesize that alpha frequency rhythmic TMS will improve behavioral performance (decreased response time) for retro-cue trials when applied to inferior-IPS; i.e. an

interaction between TMS frequency and cue.

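### Working memory capacity and spectral power are both primary, with no error control or success rule across them; if both nulls are true, the chance of a false positive primary result is about 7–10%

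*Combined protocol and SAP*

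**What the plan says.** Sections 2.3.1 and 2.3.2 each carry a primary-outcome heading, and each ends with its own null: "There is no systematic effect of frequency specific TMS on working memory capacity" and "There is no systematic effect of frequency specific TMS on spectral power". Section 11.1 repeats both labels ("Primary outcome: working memory capacity" and "Primary outcome: Spectral power") and adds a third, "Primary outcome: response time", although the heading of 2.3.3 is "SECONDARY OUTCOME – RESPONSE TIME".

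On multiplicity, 11.1 says "Post-hoc t-tests will be run on a significant main effect of TMS frequency, TMS site, or interaction", followed by "We will use Tukey's adjusted significance for post-hoc testing to correct for multiple comparisons". No section states a significance level, divides one, orders the tests, requires both primaries to succeed, or says how to read one succeeding and the other failing.

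Section 2.3 hypothesises only the interaction of TMS site and TMS frequency. Section 11.1 is looser: for frontal stimulation, the working-memory prediction may show up as a frequency main effect, as an interaction, or as both.

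**The concern.** Tukey's adjustment starts only after an ANOVA effect is significant, and it covers the pairwise tests that follow within that ANOVA. It does not govern the deciding tests themselves or the fact that there are two of them. A trial with two primary outcomes and no rule across them can be reported as positive on either one, so the error rate attached to a positive primary result is above the level used for each test.

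The two outcomes can also disagree. Spectral power is measured during and just after stimulation at the driven frequency, and it could rise without any change in memory. The plan should say in advance how that result will be described.

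**Working it through.** **1. Which alpha did section 11.2 use?** None is stated, so I worked back from its figures. Inputs from 11.2: 95% power; effect size 0.532 for the site-by-frequency interaction on working memory capacity (n = 48); 0.83 for alpha power under alpha versus arrhythmic TMS (n = 21); 0.56 for theta power under theta versus arrhythmic TMS (n = 44). I read each effect size as a standardized within-participant difference d and used a one-sample (paired) t-test.

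Power = P(|T| > t(1 − α/2; n − 1)), where T is noncentral t with n − 1 degrees of freedom and noncentrality d√n.

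For working memory capacity at n = 48: d√n = 0.532 × √48 = 3.686, the critical value at two-sided 0.05 is 2.012, and power is 95.0%. At n = 47 power is 94.6%, so 48 is the smallest n that reaches 95%.

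| Effect size | Plan's n | Two-sided 0.05 | One-sided 0.05 | Two-sided 0.025 |
|---|---|---|---|---|
| 0.532 | 48 | 48 | 40 | 56 |
| 0.83 | 21 | 21 | 18 | 25 |
| 0.56 | 44 | 44 | 36 | 51 |

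Of these settings, only unadjusted two-sided 0.05 returns all three figures. No split of alpha between outcomes was built into the sizing.

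**2. Error across the primaries when both nulls are true.**

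- Two independent tests at 0.05: 1 − (1 − 0.05)² = 1 − 0.9025 = 9.75%. Whatever the dependence, the bound is 0.05 + 0.05 = 10%.
- Correlated tests: both outcomes come from the same participants and the documents give no correlation, so I took a range. With bivariate normal test statistics the error is 9.6% at 0.2, 9.1% at 0.5, 7.8% at 0.8 and 7.0% at 0.9.
- If response time counts as a third primary, as 11.1 labels it, under independence: 1 − 0.95³ = 1 − 0.857375 = 14.3%.

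**3. Cost of controlling it with Holm.** The smaller of the two p-values is compared with 0.025. If it passes, the larger is compared with 0.05. This holds the familywise error at 5% under any correlation. For working memory capacity at n = 48 and d = 0.532:

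- Tested at 0.05 (spectral power has already passed): 95.0%.
- Tested at 0.025 (spectral power has not passed): critical value 2.315, same noncentrality 3.686, power 91.1%.

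Keeping 95% power at 0.025 would need 56 participants.

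**4. Spectral power.** The figures 0.83 and 0.56 each compare one rhythm with arrhythmic TMS in one band. The deciding test here is the interaction, and the documents give no effect size for it. No power can be stated.

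**The case against.** The strongest reply is that these are separate questions. Section 2.3 gives each outcome its own rationale, hypothesis and null, and no section says that the study succeeds if either is significant. A reader might infer that the plan lets a spectral-power result alone support a claim of improved memory. The documents do not support that: the null in 2.3.2 concerns spectral power only, so rejecting it says nothing about memory. This part of the reply stands. What remains is that the plan does not state the restriction and gives no way to read a split result.

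The study is also called a pilot in the Study Summary and section 4, and it is a mechanism study in healthy adults. That lowers the stakes. It does not remove the point, because 11.2 sizes the study for 95% power and concludes that this is enough to answer its hypotheses.

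Third, the inflation depends on conditions. If TMS truly raises spectral power, as 11.1 expects, only the working-memory null can be falsely rejected, and its risk is the ordinary 5%. With strongly correlated tests the joint error also falls well below double. Both qualifications stand and are carried into the verdict.

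Lastly, Holm is not the only remedy. A fixed testing order, or requiring both outcomes to pass, would also hold 5% with each test at 0.05. A fixed order, however, makes the second outcome depend on the first, and requiring both would turn a clear result on one into a failure. Holm lets either outcome be claimed on its own evidence, which suits the separate hypotheses in 2.3.

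**Conclusion.** The point holds: there are two primary outcomes and no error control or success rule across them. If both nulls are true and each is tested at two-sided 0.05, the chance of at least one false positive primary result is about 7–10% for correlations from 0.9 down to 0. With response time as a third primary it is 14.3% under independence.

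This rests on three assumptions: alpha is inferred from the sample sizes and not stated; the correlation is unknown; and each outcome has one deciding test.

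Two stronger readings should not be adopted. One is that the false positive risk is nearly doubled without qualification; that needs both nulls true and at most moderate correlation. The other is to count all three ANOVA effects on both primaries, which would give 1 − 0.95⁶ = 26.5% under independence. Section 2.3 hypothesises only the interaction, and the looser wording in 11.1 adds the frequency main effect for frontal stimulation, never a site main effect.

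The gap should be closed before analysis. It does not call for a redesign.

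**What to change.** In section 11.1:

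- State an overall two-sided alpha of 0.05 for the primary outcomes.
- Make the site-by-frequency interaction, expressed as the compatibility effect defined in section 2.3, the single deciding test for working memory capacity and for spectral power, and test the two with Holm.
- State that each claim is made only for the outcome that passes.
- Relabel response time as secondary, to match 2.3.3.
- Treat the main effect of TMS frequency as supportive and not as another route to success.

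The last two edits are necessary: Holm on two tests does not hold 5% if a third outcome or a second route to success stays open.

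In section 11.2, state the alpha and restate power for working memory capacity at n = 48 as 91% (tested at 0.025) to 95% (spectral power passes first). Give no power for the spectral-power interaction unless an effect size for it can be justified.

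Cost: a short rewrite of 11.1 and a sentence or two in 11.2. Power for working memory capacity falls from 95% to 91% at worst. No extra participants are needed.

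### The site-by-frequency ANOVA tests the compatibility effect, but no named test compares rhythmic TMS with arrhythmic TMS, so a claim of improvement over the active control has no test behind it

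*Combined protocol and SAP*

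**What the plan says.** **Named tests (section 11.1).** The key analysis is a two-way repeated-measures ANOVA with factors frequency (theta, alpha) and site (anterior-MFG, inferior-IPS). The data entering it are differences: "All analyses will be run on the difference from condition-matched arrhythmic TMS". Follow-up is conditional: "Post-hoc t-tests will be run on a significant main effect of TMS frequency, TMS site, or interaction", with Tukey adjustment. Cue is not a factor and arrhythmic TMS is not a level. The cue is fixed by site: "The direction of the retro-cue is held consistent for each site: for TMS to frontal cortex (anterior-MFG) the retro-cue to the right is used", and the left cue for inferior-IPS.

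**Hypotheses attached to those tests (section 11.1).** For capacity, the plan expects that "theta frequency rhythmic TMS will improve behavioral performance when applied to anterior-MFG", and equates this with "a main effect of TMS frequency and/or an interaction between TMS frequency and cue". It makes a parallel statement for alpha at inferior-IPS and repeats both for response time. For EEG it expects that "the amplitude of theta activity will be increased following theta rhythmic TMS relative to theta activity following arrhythmic TMS" and that "alpha amplitude will be increased following alpha rhythmic TMS relative to alpha amplitude following arrhythmic TMS".

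**Elsewhere.** Section 2.3 defines the compatibility effect as the compatible minus the incompatible frequency, averaged over frontal/right cue and parietal/left cue, and names the term site by frequency. Section 4.1 says that the primary analysis is rhythmic against arrhythmic TMS within a session. Section 11.2 gives N=48 for the interaction on capacity (effect size 0.532). It gives N=44 and N=21 for theta and alpha TMS against arrhythmic TMS (effect sizes 0.56 and 0.83).

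**The concern.** Two questions share one test. Section 2.3 asks whether the compatible frequency does better than the incompatible one, and the interaction answers that. Sections 4.1, 11.1 and 11.2 also ask whether rhythmic stimulation does better than the active control. Subtracting arrhythmic TMS from every cell looks as if it builds the control into the ANOVA, but the named tests then compare the subtracted cells only with each other.

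At stake is the meaning of a positive result. If theta TMS at anterior-MFG equals arrhythmic TMS and alpha TMS there is worse, the interaction can be significant. Read as section 11.1 words it, that result would be reported as improved performance when nothing had improved on the control.

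The phrase about an interaction of frequency with cue is a smaller matter. It names a term that the two-way model cannot separate from site by frequency.

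**Working it through.** **1. The plan's sample sizes.** Inputs are the effect sizes in section 11.2, read as the mean paired difference divided by its SD. Alpha and sidedness are not stated; two-sided 0.05 is assumed because it reproduces the plan. With exact noncentral-t power, the smallest n giving 95% is 48 for 0.532, 44 for 0.56 and 21 for 0.83. All three match. (One-sided tests would give 40, 36 and 18.)

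**2. Cue and site.** Code the four analysed cells, in the order frontal theta, frontal alpha, parietal theta, parietal alpha:
- site = (1, 1, −1, −1)
- cue (right = 1) = (1, 1, −1, −1)
- frequency = (1, −1, 1, −1)

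Then frequency × cue = (1, −1, −1, 1) = frequency × site. The matrix with intercept, site, frequency, site × frequency, cue and frequency × cue has rank 4 of 6. The two interactions are a single one-degree-of-freedom term.

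**3. Where the control goes.** Let t, a and r be the theta, alpha and arrhythmic means, with F frontal and P parietal, and one arrhythmic mean per site.
- Interaction: [(tF−rF)−(aF−rF)] − [(tP−rP)−(aP−rP)] = (tF−aF) + (aP−tP). This is twice the compatibility effect of section 2.3.
- Frequency effect: ½[(tF−aF) + (tP−aP)].
- Within-site post-hoc test: tF−aF, or aP−tP.

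r is absent from all three. It remains in the site effect and in cross-site pairs, but those set one site's difference against the other's. In a simulated data set of 48, replacing the arrhythmic values left F(frequency)=1.2407, F(interaction)=0.0087 and the within-site t values (0.7629, −0.7886) unchanged. The test that is not named, frontal theta minus arrhythmic, moved from t=1.97 to t=−3.06.

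This algebra applies to capacity and response time. For spectral power, cancellation also depends on which band is scored in each cell. If separate arrhythmic subsets are subtracted from theta and from alpha, r need not cancel. In neither case is a difference tested against zero.

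**4. Size.** Assume n=48, independent cell means with equal SD σ, one arrhythmic mean per site, and an effect δ at each site. The interaction has mean 2δ and SD 2σ, so δ/σ = 0.532. A direct contrast such as tF−rF has mean δ and SD √2σ, so d = 0.532/√2 = 0.376. Results from 40,000 simulated trials, with Holm over the two direct tests:

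| Truth | Interaction significant | Improvement shown, one or both sites | Improvement shown, both sites |
|---|---|---|---|
| Only the compatible frequency helps | 95% | 85% | 51% |
| Only the incompatible frequency harms | 95% | 2.5% | under 0.1% |

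**5. Power of the direct tests at n=48.**
- *Behaviour, d = 0.376:* 0.72 at 0.05 and 0.62 at 0.025.
- *Behaviour, if 0.532 came from a subtraction with two control means per site:* the interaction SD is √8σ, so 2δ/(√8σ) = δ/(√2σ) = 0.532, which is also the direct d. Power is 0.95 at 0.05 and 0.91 at 0.025.
- *EEG, the plan's effects:* theta (0.56) 96.7% at 0.05 and 93.7% at 0.025; alpha (0.83) 99.99% at 0.05.

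**The case against.** **The estimand is relative by design.** Section 2.3 defines the effect against the incompatible frequency and already ties cue to site. Benefit from one frequency and harm from the other both contradict its null hypothesis. This stands. A reader might infer that the primary test is invalid or the sample size wrong, and the documents support neither. It also means that the cue wording is a labelling error. But section 2.3 does not cover the comparison with arrhythmic TMS made in sections 4.1, 11.1 and 11.2.

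**The single-site comparison is tested.** Section 4 calls the within-participant comparison of frequencies at one site critical, and a reader might add it to the untested list. That goes too far: theta-versus-alpha post-hoc tests within a site cover it, although only after a significant ANOVA term.

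**The EEG test can be inferred.** Section 11.2 powers theta and alpha against arrhythmic TMS, and its figures reproduce as paired t-tests. For EEG the gap is therefore mainly one of formal listing. For behaviour, section 11.2 powers only the interaction.

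**Post-hoc t-tests might include tests against zero.** The wording leaves some room. Tukey adjustment, however, points to pairwise comparison of cells, and the tests are gated.

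**The harm-only case is hypothetical.** No figure in the documents supports it, and 2.5% is simply the false-positive rate that follows from setting the benefit to zero. The table shows what the tests can distinguish; it does not predict a result.

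**Conclusion.** The point holds and should be fixed before analysis. The site-by-frequency interaction and N=48 stand as the test of section 2.3. What lacks a named test is the comparison with arrhythmic TMS, which section 4.1 calls primary and on which any statement of improvement over the active control depends. With one control mean per site, the frequency and interaction terms for capacity and response time cannot separate benefit from harm.

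The simulated sizes assume equal independent cell noise, effects of the same size at both sites, and two-sided 0.05. The 85% is for improvement at one or both sites. The plan hypothesises improvement at both, where the figure is about 51%, and it rises if 0.532 already reflects a subtraction with two control means per site. A reader might also infer that subtracting separate control subsets leaves the interaction underpowered. The documents do not settle this: power stays at 0.95 if 0.532 was obtained that way, and section 11.2 does not say how it was.

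**What to change.** 1. Keep site by frequency as the powered test. Replace the references in section 11.1 to an interaction of frequency with cue by the site-and-cue compatibility interaction.
2. For each outcome, prespecify two one-sample tests against zero: theta minus arrhythmic at anterior-MFG (right cue) and alpha minus arrhythmic at inferior-IPS (left cue). For EEG, score them in theta and alpha power respectively, as in section 2.3.2. Apply Holm within outcome, do not gate the tests on the ANOVA, and keep them separate from the Tukey post-hoc tests. Claim improvement over active control only where the relevant test is significant in the hypothesised direction (a decrease for response time).
3. State which arrhythmic trials are subtracted from theta and which from alpha, since this decides whether the control cancels.

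The cost is SAP wording and two contrasts per outcome on data already planned, with no change to stimulation or sample size. The downside is modest behavioural power: 0.62 to 0.72 per site at d = 0.376, or 0.91 to 0.95 under the two-control-mean reading. A non-significant direct test should therefore not be read as showing no benefit. For EEG, only theta at the stricter Holm step (93.7%) falls slightly below the plan's 95%.
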